## 10.5 Borg CR 10 Scale® or Modified Borg Dyspnoea Scale

In context with 12934 protocol amendment 4 the “Modified Borg Dyspnoea Scale” was replaced by the Borg CR 10 Scale®. For consistency reason, patients who were enrolled before approval of 12934 protocol amendment 4 in their country must use the “Modified Borg Dyspnoea Scale” throughout the main and the extension study.

The Borg CR 10 Scale or the Modified Borg Dyspnoea Scale will always be measured in conjunction with the 6MWD Test.

The Borg CR 10 Scale or the Modified Borg Dyspnoea Scale will be explained to the patients before starting the 6MWD Test (questionnaires and instructions will be provided in local language). Patients will be asked to rank their exertion at the end of the 6MWD Test. If a patient has problems to understand the principles of rating, an attempt should be made to explain the principles in a neutral and unpersuasive manner.

The test result will be entered on same work sheet as the 6MWD Test result Later on the results will be transferred into the electronic CRF.

### 10.5.1 Borg CR 10 scale and test instructions

CCI [REDACTED]

[REDACTED]

[REDACTED]

[REDACTED]

[REDACTED]

[REDACTED]

[REDACTED]

[REDACTED]

[REDACTED]

[REDACTED]

[REDACTED]

[REDACTED]

[REDACTED]

[REDACTED]

[REDACTED]

CCI [Redacted]

[Redacted]

[Redacted]

[Redacted]

[Redacted]

[Redacted]

[Redacted]

[figure not shown]
[Redacted]

[Redacted]

[Redacted]

CCI [Redacted]

CCI

### 10.5.2 Modified Borg Dyspnoea Scale

CCI

CCI

CCI  
[Redacted]

## 10.6 WHO functional class

The patient's functional class will be determined by using the WHO classification (Class I- IV / refer to [American College of Chest Physicians. Diagnosis and Management of Pulmonary Arterial Hypertension: ACCP Evidence-Based Clinical Practice Guidelines. Chest 2004; 126; 7-10s](#)):

I: Patients with PH but without resulting limitation of physical activity. Ordinary physical activity does not cause undue dyspnoea or fatigue, chest pain, or near syncope.

II: Patients with PH resulting in slight limitation of physical activity. They are comfortable at rest. Ordinary physical activity causes undue dyspnoea or fatigue, chest pain, or near syncope.

III: Patients with PH resulting in marked limitation of physical activity. They are comfortable at rest. Less than ordinary activity causes undue dyspnoea or fatigue, chest pain, or near syncope.

[figure not shown]
IV: Patients with PH with inability to carry out any physical activity without symptoms. These patients manifest signs of right-heart failure. Dyspnoea and/or fatigue may even be present at rest. Discomfort is increased by any physical activity.

## 10.7 EQ-5D

CCI  
[Redacted]  
[Redacted]  
[Redacted] The EQ-5D is a self-report questionnaire and needs to

[figure not shown]
be completed by the patient (questionnaires will be provided in local language). However, if the patient has problems completing the questionnaire, an attempt should be made to explain the questions in a neutral and unpersuasive manner.

After the patient has filled in the questionnaire, the questionnaire is transferred to the study personnel, who will enter the content into the electronic CRF.

CCI

## 10.8 Living with Pulmonary Hypertension questionnaire (LPH)

[figure not shown]
CCI

The LPH is a self-report questionnaire and needs to be completed by the patient (questionnaires will be provided in local language). However, if the patient has problems completing the questionnaire, an attempt should be made to explain the questions in a neutral and unpersuasive manner.

After the patient has filled in the questionnaire, the questionnaire is transferred to the study personnel, who will enter the content into the electronic CRF.

CCI

## **10.9 Role of the Steering Committee (SC)**

The Steering Committee has the overall scientific responsibility of the study. It will guide the trial in all aspects of safety and efficacy and has to assure that all relevant information coming from the sponsor (e.g. from the Global Pharmacovigilance department), from other study committees (e.g. from the Data Monitoring Committee) and from the investigators will thoroughly be reviewed and all relevant decisions with regard to the conduct will be taken in due time. In particular the Steering committee has the following responsibilities:

- Primary responsibility for designing the study
- Primary responsibility for the content of protocol amendments
- To ensure a scientifically sound and safe conduct of the study
- To decide on Data Monitoring Committee recommendations together with the sponsor
- Primary responsibility for the final study report

## **10.10 Role of the Data Monitoring Committee (DMC)**

It is the main responsibility of the Data Monitoring Committee (DMC) to protect the safety of the patients participating in the BAY 63-2521 phase III program. In this context, the DMC will regularly review accumulating study data with the responsibility to provide an independent recommendation on the advisability of continuing the study as planned.

The DMC will conduct its reviews based on unblinded data summaries. During the course of the trial the DMC and the SC should closely interact and alert each other in order to assess all safety relevant information. The DMC should also closely interact with the sponsor's Global Pharmacovigilance department.

In case of unacceptable safety profile, the DMC can recommend to stop the trial. However, the final decision will be made by the SC together with the sponsor.

DMC will stop when all patients are on open label dose of Riociguat (changed with amendment 11).

For further details refer to the DMC Charter.

NT pro-BNP	N-terminal pro-brain natriuretic peptide
PAH	Pulmonary arterial hypertension
PAP	Pulmonary artery pressure
PDE5I	Phosphodiesterase type 5 inhibitors
PH	Pulmonary Hypertension
PPI	Proton pump inhibitor
PVR	Pulmonary vascular resistance
SAS	Statistical Analysis System
TID	ter in die (3 times a day)
WHO	World Health Organization
WHO-DD	World Health Organization – Drug Dictionary

1. Introduction

This SAP for the final analysis is based on the following study protocol versions:

- 12935 / version 2.0, 11 September 2008
- Amendment 1 (Japan) / Version 1.0 / 01 Oct 2008
- Amendment 2 (UK) / Version 1.0 / 08 Jan 2009
- Amendment 3 (NZ) / Version 1.0 / 18 Mar 2009
- Amendment 4 (Spain) / Version 1.0 / 09 Jun 2009
- Amendment 5/ Version 1.0 / 10 Jun 2009
- Amendment 6/ Version 1.0 / 22 Mar 2010
- Amendment 7 (Japan) / Version 1.0 / 23 Mar 2010
- Amendment 8 / Version 1.0 / 15 Feb 2011
- Amendment 9 (US, CAN) / Version 1.0 / 28 Feb 2011
- Amendment 10 / Version 1.0 / 30 Nov 2011

Reference Number: RD-OI-0119

Supplement Version: 8

- Amendment 11/ Version 1.0/ 13 DEC 2012
- Amendment 12 (Korea)/ Version 1.0 / 03 APR 2013
- Amendment 13 (China)/Version 1.0/ 08 JUL 2014
- Amendment 14 (France)/ Version 1.0/ 28 OCT2015

There is a set of global and project standard tables. References are given in the TLF specifications document associated with this SAP.

2. Study Objectives

To assess the long-term safety and tolerability of riociguat in treatment naive patients and patients pretreated with an Endothelin Receptor Antagonist or a Prostacyclin Analogue with symptomatic Pulmonary Arterial Hypertension (PAH). The trial provides patients, who have completed 12 weeks of riociguat double blind treatment (PATENT-1, study 12934), the option of long-term treatment with riociguat.

For this study it is planned to enroll subjects in the following countries:

United States of America, Canada, Sweden, Denmark, Norway, China, Singapore, Taiwan, South Korea, Austria, Germany, Switzerland, Netherlands, Belgium, France, Italy, Spain, Ireland, South Africa, United Kingdom, Argentina, Brazil, Mexico, Australia, New Zealand, Japan, Czech Republic, Poland.

A list of countries that actually enrolled patients will be given.

3. Study Design

This is an open-label, multicenter, multinational, long-term extension (blinded with respect to dose up to Visit 5 [end of titration phase], in order to maintain the blinding of the PATENT-1 study).

All subjects entering the extension study first participated in a blinded 8-week titration phase. The dose of riociguat was increased, maintained, or decreased depending on whether peripheral systolic blood pressure (SBP) was ≥ 95 mmHg, 90 – 94 mmHg, or < 90 mmHg, in accordance with the following rules:

- Subjects from the former placebo group of the PATENT-1 study started at Visit 1 with a riociguat dose of 1.0 mg tid. The individual riociguat dose was up-titrated in steps of 0.5 mg tid every 2 weeks up to a maximum of 2.5 mg tid.
- Subjects from the former riociguat 1.0–1.5 mg tid capped dose titration group of PATENT-1 entered the extension trial on the same dose level as they received on the last day of PATENT-1. Subjects whose last dose in PATENT-1 was 1.0–1.5 mg tid were up-titrated in steps of 0.5 mg tid every 2 weeks up to a maximum of 2.5 mg tid. Subjects whose last dose in PATENT-1 was 1.0 mg or 0.5 mg tid underwent sham titration, with no increase in dose of study drug before the end of the titration phase.
(titration approach modified by protocol amendment 5)
- Subjects from the former riociguat 1.0-2.5 mg tid group of PATENT-1 entered the extension trial on the same dose level as they received on the last day of PATENT-1. Subjects underwent sham titration, with no increase in dose of study drug before the end of the titration phase.

Reference Number: RD-OI-0119

Supplement Version: 8

During the main study phase, investigators (unblinded to dose) could modify the riociguat dose in a range between 0.5 mg tid and 2.5 mg tid according to the subject's need.

Dose reductions for safety reasons were allowed at any time.

For further details see integrated study protocol, amendment 11, version 1.0, Section 4.1.

4. General Statistical Considerations

4.1 General Principles

The statistical evaluation will be performed by using the software package SAS release 9.2 or higher (SAS Institute Inc., Cary, NC, USA). All variables will be analyzed by descriptive statistical methods. The number of data available and missing data, mean, standard deviation, minimum, quartiles, median, and maximum will be calculated for metric data. Frequency tables will be generated for categorical data.

4.2 Handling of Dropouts

There is no definition of dropouts in the CSP.

4.3 Handling of Missing Data

Although efficacy variables will be summarized in a purely descriptive manner, imputation for missing values will still be made, for comparability of the results with study 12934, at week 12 and end of study. The imputation to the end of the study will only be done at the conclusion of the extension study.

For subjects completing the study as planned, the measurements taken at the end of study will be used. However, should a subject stop the study medication prematurely, the values recorded at the termination visit will be used.

Where a subject dies or withdraws due to clinical worsening with no subsequent visit, the following rules will be used: 6MWD worst possible value (0 m), Borg CR 10 Scale[®] worst possible value (10), EQ-5D and LPH worst possible score. Death or withdrawal due to clinical worsening are components of time to clinical worsening, so will be included as an event by definition. For WHO functional class, in the case of withdrawal due to clinical worsening with no termination visit, the worst possible score (IV) will be used, in the case of death the worst possible value plus one (V).

In the case of withdrawal for other reasons with no post-baseline measurements, the baseline will be taken. If the subject completes the study as planned, but there is no efficacy measurement at the end of the study, the last post-baseline value will be used.

PVR and NT pro-BNP are efficacy measures designed to show the direct effects of study treatment on biomarkers, and so it would not be appropriate to use an imputation rule in the case of death or missing post-baseline data. In the case of premature stop of study medication, measurements taken at the termination visit or last visit post-baseline will be used.

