## Events of Special Interest

### Time To Clinical Worsening

The first occurrence of the following events of special interest need to be documented in the electronic CRF and will be considered for the calculation of the combined endpoint “Time To Clinical Worsening”:

- Death (all-cause mortality)
- Heart/lung transplantation
- Atrial septostomy (AS)
- Hospitalization due to persistent worsening of Pulmonary Hypertensiona,b
- Start of new PH specific treatment (Endothelin Receptor Antagonists, Prostacycline Analogues, Phosphodiesterase Type-5 Inhibitors) or modification of a preexisting Prostacycline Analogues treatment (ie increase of number of daily Iloprost inhalations from 6 to 9, or increase of Iloprost dosage from 2.5 to 5.0 microgram per inhalation, or start of an iv Prostacycline Analogue) due to worsening Pulmonary Hypertension.
- Persistent decrease of more than 15 % from baseline or more than 30% compared to the last study related measurement in 6MWD due to worsening pulmonary hypertensionb.

The persistence of the decrease has to be confirmed by a second measurement performed after 14 days. In case that the period between first occurrence of the event and the Termination Visit is less than 14 days, the decrease needs to be confirmed at the Termination Visit.

- Persistent worsening of functional class due to deterioration of Pulmonary Hypertensionb:

Patients who deteriorate from class II or III to class IV: The persistence of worsening has to be confirmed by a second measurement performed after 14 days. In case that the period between first occurrence of the event and the Termination Visit is less than 14 days, the decrease needs to be confirmed at the Termination Visit.

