### **Other Events of Special Interest**

The first occurrence of the following event of special interest needs to be documented in the electronic CRF, but will not be considered for the calculation of the combined end point “Time To Clinical Worsening”:

- Initiation of a supplemental long-term oxygen therapy (= oxygen application for more than 30 days at a stretch) or persistent modification of a pre-existing supplemental long term oxygen therapy (ie need for a persistent increase of the amount of delivered oxygen for more than 30 days) due to worsening pulmonary hypertension.b

aTransient deteriorations of clinical status requiring hospitalization, treatable by eg short time application of iv diuretics, positive inotropic agents or non-invasive ventilation and allowing patients discharge within 48 hours are not considered as persistent with respect to the event of special interest definition.

bIn case of clinical deterioration the investigator has to assess carefully if the deterioration of the patient’s condition (eg worsening functional class) is related to the underlying pulmonary hypertension or can be explained by an alternative cause (eg transient infection, musculoskeletal disease, surgical or medical intervention other than PH related, exacerbation of a concomitant lung disease, lacking compliance of medication intake). Only persistent clinical deteriorations caused by the underlying pulmonary hypertension will be considered as events of special interest.

Frequency: At every visit with the exception of Visit 1 and Safety Follow-Up Visit the investigator must check if an event of special interest has occurred in the period between start and termination of the study drug treatment. With respect to each subcategory (eg “hospitalization due to persistent worsening of pulmonary

hypertension”) it is only necessary to document the first occurrence of such an event in the electronic CRF.

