6.2 Efficacy

Efficacy variables are:

- 6 minute walking distance from the 6MWT
- PVR (no RHC required at any time during study, PVR only measured if RHC performed as part of regular diagnostic work up)
- NT pro-BNP
- WHO functional class
- Time to clinical worsening
- Borg CR 10 Scale[®]
- EQ-5D questionnaire
- LPH questionnaire

In the efficacy analyses, countries and centres will be clustered by geographic region, consistent with the pooling in study 12934.

All analyses will be descriptive. For non-categorical data, absolute values and changes from baseline will be summarized. Baseline will be week 0 of study 12934.

It is envisaged that WHO functional class will either remain the same, improve by one or two categories, or deteriorate by one category in most cases. A change score (end of study minus baseline) will be calculated, which could go from -3 (class IV at baseline and class I at end of study) to +4 (class I at baseline, death at end of study), but in practice for those patients still alive at the end of the study it will most likely range from -2 to +1

Time to clinical worsening is made up of several components:

- 1) all-cause mortality
 - 2) heart/lung transplantation
 - 3) Atrial septostomy (AS)
 - 4) hospitalization due to persistent worsening of pulmonary hypertension
 - 5) start of new PH-specific treatment
 - 6) persistent decrease in 6MWD
 - 7) persistent worsening of functional class
- as defined in the protocol section 4.6.4.

The occurrence of the event of clinical worsening during the long-term extension will be summarized using categorical methods, but as an additional summary, the time to event will also be described. In determining whether an event is considered to be an event of clinical worsening the same rules as in study 12934 will be applied.

Change in the Borg CR 10 Scale[®] will be summarized using frequency counts.

The exploratory efficacy variables described in the Supplementary SAP of study 12934 will be summarized descriptively. This includes the subscales of the EQ5D and LPH and the additional haemodynamic variables. Also the sensitivity analysis of clinical worsening and the categorical analyses described in the Supplementary SAP of study 12934 will be performed.

The primary and secondary efficacy variables, except PVR, will be summarized descriptively for the following subgroups:

- therapy-naïve
- pre-treated
- pre-treated with Endothelin Receptor Antagonist
- pre-treated with Prostacyclin Analogue
- region

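### SAP 4.3 makes withdrawal due to clinical worsening a clinical-worsening event by definition, but it is not among the seven components in SAP 6.2 and protocol 4.6.4

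*SAP*

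**What the plan says.** Three places define the event.

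- **SAP 4.3 (Handling of Missing Data).** The paragraph gives worst-value imputation for a defined group: "Where a subject dies or withdraws due to clinical worsening with no subsequent visit". Within it stands the sentence "Death or withdrawal due to clinical worsening are components of time to clinical worsening, so will be included as an event by definition".
- **SAP 6.2 (Efficacy).** "Time to clinical worsening is made up of several components", followed by seven numbered items, "as defined in the protocol section 4.6.4". The section adds: "In determining whether an event is considered to be an event of clinical worsening the same rules as in study 12934 will be applied".
- **Protocol 4.6.4 (Time To Clinical Worsening).** This lists the events that "will be considered for the calculation of the combined endpoint", and they are the same seven. For walking distance, "The persistence of the decrease has to be confirmed by a second measurement performed after 14 days", or at the Termination Visit if that falls sooner; functional class has a parallel rule. A footnote adds: "Only persistent clinical deteriorations caused by the underlying pulmonary hypertension will be considered as events of special interest".

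Protocol 6.1 reports the endpoint as an overall rate, a table of the event that led to worsening, and a Kaplan-Meier curve.

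**The concern.** SAP 4.3 treats withdrawal for worsening as a component in its own right, while the two lists that define the endpoint omit it. The conflict falls on patients who leave because they are deteriorating, the group a worsening endpoint is meant to describe. All three reported outputs depend on which sentence the programmer follows. A patient counted only through SAP 4.3 would also have no category in the breakdown by leading event and no defined event date.

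**Working it through.** The plan states no figure that can be reproduced here: no event count, expected rate or sample size (protocol 6.2 marks sample size as not applicable). The check compares the texts and traces patients through them.

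**1. Compare the lists.**

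| Item | SAP 6.2 | Protocol 4.6.4 | SAP 4.3 |
|---|---|---|---|
| Death from any cause | yes | yes | death named as an event |
| Heart/lung transplantation | yes | yes | – |
| Atrial septostomy | yes | yes | – |
| Hospitalization for persistent PH worsening | yes | yes | – |
| New PH-specific treatment | yes | yes | – |
| Persistent fall in walking distance | yes | yes | – |
| Persistent functional-class worsening | yes | yes | – |
| Withdrawal due to clinical worsening | **no** | **no** | **event by definition** |

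The lists agree with each other, 7 items to 7. Withdrawal appears in 0 of 7 in each.

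**2. Trace patients through both rules.**

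- *Patient A* has a first walking-distance fall of more than 15% from baseline, or a first move to class IV, then withdraws for worsening with no later visit and no other listed event. The second measurement does not exist. The worst values that SAP 4.3 imputes (0 m, class IV) are not measurements and cannot confirm the decline. SAP 4.3: event. Component list: no event.
- *Patient B* goes from class II to class III and withdraws for worsening with no later visit and no other listed event. The protocol's functional-class component covers only moves from II or III to IV. SAP 4.3: event. Component list: no event.
- *Patient C* is hospitalized for persistent PH worsening and then withdraws. Event under both rules.

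Only patients like A and B are affected.

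**3. Size.** Let N be the number treated and m the number withdrawn for worsening with no later visit and no listed event, with w = m/N. If E patients have a listed event:

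- crude incidence by the list = E/N
- crude incidence by SAP 4.3 = (E + m)/N
- difference = m/N = w

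The documents give none of E, m or N. As a pure assumption, w of 0%, 1% and 5% gives differences of 0, 1 and 5 percentage points.

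On the Kaplan-Meier curve, a patient leaving when n are at risk (no ties) multiplies the estimate by (n − 1)/n under SAP 4.3 and by 1 under the list. The shift therefore depends on when these patients leave and is not exactly w.

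**The case against.** **The sentence may only explain why this endpoint needs no imputation.** That is a fair account of why it sits in a missing-data section. It does not remove the conflict, because the sentence says withdrawal is itself a component.

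**Withdrawal for worsening may presuppose a listed event.** Much of this stands. Death, PH hospitalization and new PH-specific treatment count under both rules. Starting a PDE5 inhibitor for worsening PH is a listed event and also requires stopping study drug, so many such withdrawals may already be captured. The overlap is not guaranteed, however. Protocol 4.5.7 places the PDE5 inhibitor start at least 24 hours after the last dose. Protocol 4.6.4 checks for events between start and termination of study drug and exempts the Safety Follow-Up Visit, although the flow chart in 10.1 marks event evaluation there. Patients A and B also remain.

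**The study 12934 rules may settle it.** They may, but neither document reproduces them. If they count withdrawal, the SAP 6.2 list is incomplete; if they do not, SAP 4.3 is wrong. One text needs correcting either way. A reader might infer that SAP 4.3 breaks comparability with 12934, but that cannot be concluded without those rules.

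**A sensitivity analysis already exists.** SAP 6.2 carries over the clinical-worsening sensitivity analysis from the 12934 supplementary SAP. Its content is not shown, so a further one may be unnecessary.

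**The endpoint is secondary to safety.** The study has no primary variable and no comparator, and SAP 6.2 calls the time-to-event description an additional summary. This limits the consequence, but a descriptive rate still needs one event definition.

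**Conclusion.** The inconsistency is real and should be corrected. Its reach is narrow: patients withdrawn for worsening who have no later visit and meet none of the seven components. For them the two rules give opposite answers, and crude incidence differs by w, which is unknown and may be close to zero. That a non-event is censored is an inference: neither document states a censoring rule, but a Kaplan-Meier analysis leaves no other treatment.

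A reader might infer more, in three ways the documents do not support:

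- *That a decline first seen at the Termination Visit is caught in the same conflict.* Such a patient has a later visit and so falls outside the group SAP 4.3 addresses, and protocol 4.6.4 is unclear on whether that visit can confirm the decline.
- *That the reported rate would rise substantially.* No count or baseline rate is available, so any relative increase would rest wholly on assumed inputs.
- *That SAP 4.3 waives the search for another cause of the deterioration.* It does not say so; protocol 4.6.4 asks the investigator to make that assessment for any clinical deterioration.

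No error rate, power or decision rule is affected.

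**What to change.** Replace the SAP 4.3 sentence with: *All-cause death is a component of time to clinical worsening and is an event; withdrawal due to clinical worsening is an event only if one of the seven components in protocol 4.6.4 is met.* Merely deleting the reference to withdrawal would not do, because what is left could be read as limiting death to death from worsening, against the all-cause component.

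Report withdrawal for worsening without a listed component as a separately labelled sensitivity row, dated at stop of study drug, unless the 12934 sensitivity analysis already planned in SAP 6.2 covers it. The row needs a stated definition: the withdrawal reasons in protocol 4.3 do not name clinical worsening, and the documents do not show that it is recorded as a disposition reason.

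If the 12934 rules do count such withdrawals, add the item to the SAP 6.2 list instead, with a definition, an event date and a table row, and state the departure from protocol 4.6.4.

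The cost is one corrected sentence and at most one extra table row, plus a check of the 12934 rules. If the eCRF does not record the reason directly, identifying the patients for the row will take some review.

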### **Termination Visit**

In case the decision has been made to stop the study medication prematurely or if the sponsor announces the official end of the study, a Termination Visit should be performed at the respective point in time or as soon as possible after stop of medication. In general, at the Termination Visit the same efficacy and safety relevant measurements should be performed as at Visit n (Exception: no pregnancy test needs to be performed). In particular, every effort should be made to perform the 6MWD Test. Deviations need to be documented in the electronic CRF.

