### **HEOR measurements**

#### **EQ-5D, LPH**

EQ-5D and LPH are health questionnaires that evaluate the patient’s health status and quality of life.

Methodology: Questionnaires need to be self-completed by the patients

EQ-5D Frequency: V5 and V6 only

LPH Frequency: Visit 5 only.

For further details refer to Section [10.7](#) and Section [10.8](#).

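### SAP 4.3 builds end-of-study EQ-5D and LPH values although the Amendment 11 schedule stops them at V6 and V5, and it leaves some early stoppers with no rule on any scale that has a worst value

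*SAP*

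**What the plan says.** SAP 4.3 keeps imputation although the analysis is descriptive, "for comparability of the results with study 12934, at week 12 and end of study". For 6MWD, the Borg CR 10 Scale, EQ-5D, LPH and WHO functional class it works by type of patient:

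- Finishes as planned: the end-of-study measurement. Failing that, if "there is no efficacy measurement at the end of the study, the last post-baseline value will be used".
- Stops early: "should a subject stop the study medication prematurely, the values recorded at the termination visit will be used".
- Dies, or withdraws for clinical worsening, and has no later visit: the worst value of the scale. For WHO class this is IV on withdrawal and V on death.
- Withdraws for another reason: "In the case of withdrawal for other reasons with no post-baseline measurements, the baseline will be taken".

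PVR and NT-proBNP are treated separately. Nothing is imputed for death or for absent post-baseline data, but after an early stop "measurements taken at the termination visit or last visit post-baseline will be used". SAP 4.5 writes the imputed results into the efficacy datasets.

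The protocol, with Amendment 11 incorporated, states in 4.6.4: "EQ-5D Frequency: V5 and V6 only" and "LPH Frequency: Visit 5 only". Section 4.6.3 adds that "at the Termination Visit the same efficacy and safety relevant measurements should be performed as at Visit n". The flow chart in 10.1 marks neither questionnaire at V7–Vn or at Termination.

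**The concern.** Protocol 4.6 includes efficacy in order to indicate whether the effect lasts under long-term treatment. A reader would look to the end-of-study summary for that. On the Amendment 11 schedule, EQ-5D and LPH entries in such a summary would not be late measurements. They would be values from the first 12 weeks of the extension, together with worst scores assigned by rule. The SAP lists Amendment 11 in section 1 and records in 6.4 that it removed laboratory testing, but 4.3 was not adapted to the shorter questionnaire schedule. At stake is what a descriptive table appears to show. Protocol 6.1 names no single primary variable and makes all analyses descriptive, so no error rate is involved.

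**Working it through.** The plan gives no figure to reproduce here, and Protocol 6.2 has no sample size. The check sets the schedule beside the imputation rules.

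**Step 1. Schedule against rule** (Protocol 4.6.3, 4.6.4 and 10.1; SAP 4.3)

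| Scale | Last routine visit | At V7–Vn and Termination? | Worst value in SAP 4.3? |
|---|---|---|---|
| 6MWD | continues | yes | yes |
| WHO functional class | continues | yes | yes |
| EQ-5D | V6, day 84 | no | yes |
| LPH | V5, day 56 | no | yes |
| Borg | V6, day 84 | no (see the 10.5 wording under the objections) | yes |
| NT-proBNP | V6, day 84 | no | no; last value carried after early stop |

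Of the five scales with a worst value, two are still measured at the visits from which an end-of-study value would come.

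**Step 2. EQ-5D and LPH for a patient ending after V6 on this schedule**

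- Finishes as planned: no end-of-study value is scheduled, so the last post-baseline value is used. That is day 84 or earlier for EQ-5D and day 56 or earlier for LPH.
- Dies, or withdraws for worsening, with no later visit: worst score.
- Withdraws for another reason and has a V5 or V6 value: the rule points to a Termination value that is not scheduled. The baseline rule needs post-baseline data to be absent. The last-value rule covers only patients who finish as planned. The fallback to the last visit is written only for PVR and NT-proBNP. No rule is left.
- Withdraws for worsening but attends Termination: the worst-score rule does not apply, and again there is no value and no fallback.

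The third case is a gap in the wording of 4.3 itself. It also reaches 6MWD and WHO functional class when the Termination measurement is missed. For those two it depends on a missed test. For EQ-5D and LPH the schedule produces it.

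**Step 3. Week 12.** EQ-5D has a week-12 visit (V6). LPH does not. SAP 4.3 imputes at week 12 but does not say how a week-12 LPH value would be formed.

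**Step 4. Age of a carried value, for illustration only**

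Wholly on the Amendment 11 schedule, with T years of treatment assumed:

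- EQ-5D: T × 365.25 − 84 = 281, 1,012 and 1,742 days at T = 1, 3 and 5.
- LPH: T × 365.25 − 56 = 309, 1,040 and 1,770 days at T = 1, 3 and 5.

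For a patient already past V6 when the site changed to Amendment 11, the last scheduled value cannot be later than that change. From 13 Dec 2012 (Amendment 11) to 28 Oct 2015 (Amendment 14, France) is 730 + 319 = 1,049 days. With an assumed local delay of 0, 6 or 12 months, a completer ending on the later date would carry a value at least 1,049, 866 or 684 days old. This assumes that Amendments 12 to 14 did not restore the questionnaires.

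**The case against.** The strongest case on the other side is that these are secondary descriptive summaries. Protocol 6.1 already plans summaries at each visit, which show where measurement stops, and SAP 4.1 asks for counts of available and missing data. The table layouts are in a TLF specification that is not among the documents, so whether a table would mislead cannot be seen directly. This stands as a limit on severity. It does not remove the problem: nothing in 4.3 requires the time of a carried value to be shown, and 4.1 does not say whether an imputed value counts as available.

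Comparability with study 12934 is a stated aim, and a worst score for death is a deliberate choice. Both stand. They support a week-12 EQ-5D value; they do not turn it into a late one.

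Several stronger readings are tempting but not supported:

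- A reader might infer that every end-of-study value is years old. The schedule before Amendment 11 is not in the documents, so patients followed earlier may have later values. No passage shows that anyone was treated wholly on the current schedule. The 1,049 days rest on an amendment for one country.
- A reader might infer that the protocol contradicts itself on Borg, because 10.5 ties the scale to every 6MWD Test without exception. Section 4.6.4, the flow chart and the visit details all stop Borg at V6, and 10.5 can be read as saying how Borg is done rather than when. It needs clarifying.
- A reader might infer that LPH from V5 becomes the week-12 value. The last-value sentence covers only a missing end-of-study measurement.
- A reader might infer that 6MWD and WHO functional class are untouched. That is true of the schedule gap, but not of the missing early-stopper rule.

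**Conclusion.** The point holds on the text. On the Amendment 11 schedule, SAP 4.3 creates end-of-study EQ-5D and LPH values for patients who end after V6 with no scheduled measurement behind them, and NT-proBNP for early stoppers has the same weakness. Separately, 4.3 has no rule for withdrawal for other reasons with post-baseline data but no Termination value, on any of the five scales with a worst value. The size cannot be determined: the earlier schedule, the study end date and the number of patients in each category are not given, so the figures in days are illustrations under stated assumptions. The consequence is a table that could be mistaken for measured long-term status. It is worth correcting before the final tables are produced, but it does not touch the safety objective.

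**What to change.** In SAP 4.3:

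1. Limit end-of-study imputation to 6MWD and WHO functional class.
2. Summarise EQ-5D, NT-proBNP and Borg by visit to V6 and LPH to V5, as Protocol 6.1 already provides, plus any later values collected before the amendment. Alternatively, keep a table titled *last available value* and show the time of that value.
3. State one early-stopper rule for every scale still imputed: the Termination value, otherwise the last post-baseline value. SAP 4.3 already does this for PVR and NT-proBNP.
4. Show LPH at week 8, not week 12.
5. Clarify whether Protocol 10.5 is meant to extend Borg beyond the V6 limit in 4.6.4 and 10.1. If Borg was collected with every 6MWD Test, it may stay in the end-of-study imputation.

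The cost is SAP wording and one derivation flag, with no new data. The price is that there is no end-of-study EQ-5D or LPH table, or only a relabelled one, and less comparability with study 12934, which is the SAP's reason for imputing.
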